16.2 Sample size

The sample size calculation is based on two co-primary outcomes [36] :

1. 28-day mortality, for which we want to show non-inferiority of the PCT guided assessment as compared to current standard practice, using an absolute 2.5% non-inferiority margin. Assuming a 28-day mortality of 15% in patients managed as suspected sepsis treated in the ED [3, 12], this means that any increase in 28-day mortality from 15% to not more than 17.5% would be considered non-inferior. For

90% power and one-sided 5% significance level the sample size required is 7002, assuming there is no difference in 28-day mortality between arms. Our patient focus group were also consulted on the 2.5% non-inferiority margin and felt that this was acceptable if there were mechanisms to monitor trial outcomes, and if this was what was needed to provide a sample size which would ensure the trial could be completed as well as answer the research question.

2. Initiation of antibiotics treatment, for which we want to show superiority. Currently around 90% of patients managed as suspected sepsis receive antibiotics (RLBUHT, unpublished data). A reduction by 10 percentage points to 80% would be considered a success. To detect such an effect with 90% power and two-sided 5% significance level the sample size required is 532, which is substantially lower than what is needed for the non-inferiority endpoint. With 7002 patients we would be able to detect effects as small as a reduction from 90% to 87.6% prescriptions, with 90% power.

Accounting for 5% dropout, we need a total sample size of 7372. We include one interim analysis (after 50% of patients have provided data) with options to stop the trial early using group-sequential O'Brien-Fleming boundaries [37, 38]. We will consider stopping for effectiveness if:

- the PCT guided assessment is superior in terms of 28-day mortality (i.e. a significant reduction to less than 15%), or
- the PCT guided assessment is non-inferior in terms of 28-day mortality and superior in terms of initiation of antibiotics.

We will consider stopping for futility if the results of the interim analysis suggest futility for both endpoints.

The group-sequential design will increase the total maximum sample size (if the study is not stopped after the interim analysis) by just over 4% to 7676 (inflated for 5% dropout). However, the sample size will be substantially smaller if the trial does get stopped early.

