18.2 Health Economics

Economic analyses of the project have been planned based on expected primary and secondary outcomes of health intervention. As per the primary research question of the project, we expect that in ED patients managed as suspected sepsis, the addition of PCT to the NEWS2 scoring measurement may lead to a reduction in antibiotic initiation with at least no increase in 28-day mortality compared to the NEWS2 scoring alone. The secondary research question considers a broader aspect of economic evaluation that includes the societal perspective including the preferences of patients and family members. So, it examines if the proposed intervention would be cost-effective from the societal perspective (including household consequences).

In economic analyses, we shall apply NHS and societal perspective to address the decision making in the health system and on the society respectively. They will follow the intention-to-treat of the primary clinical effectiveness and safety analyses. Missing economic data will be imputed in a standard manner. The costs borne by NHS and the patients will thus be considered in estimations wherever applicable.

- 1) Cost of illness per patient from sepsis in intervention arm (IA: PCT + NEWS2) and standard care arm (SCA: NEWS2 alone), from the NHS and patient household perspectives.
- 2) Cost-saved per unit investment into proposed IA due to avoided antibiotic prescription, reduction of hospitalizations, and other cost-savings
- 3) Cost-effectiveness analysis of proposed intervention (PCT + NEWS2) in comparison to standard care per life year saved and £ per QALY gained
- 4) Cost-benefit analysis of proposed intervention (PCT + NEWS2)

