Here, the net cost of intervention is to be compared with the cost saved on avoidable antibiotics to estimate the money saved per GBP invested in the intervention arm. The outcome data of the intervention in terms of antibiotic avoided will be collected from a comparison of the two arms. The difference in antibiotic prescribing (number of patients and dosages) for patients between IA and SCA will be recorded from the ED and hospital prescription records. The unit price of antibiotic per dose will be multiplied by the doses avoided. Together with the savings due to reduced hospital admissions this will capture the total costs of antibiotic avoided due to the proposed intervention. The costs of intervention will be captured by identifying and quantifying the inputs used for patients in IA and SCA, valuing the inputs into economic costs with necessary (if applicable) adjustments for time preferences [42]. Such costs of intervention from the existing UK study by Hex et al. [43] might be used if not available in the reporting hospitals. Incremental costs between IA and SCA will constitute the investment on the proposed intervention for comparing with costs saved due

to reduced antibiotic use. It should be noted here that this intervention cost will be used in the cost-effectiveness analysis (CEA) (point 3 below) and cost-benefit analysis (CBA) (point 4 below) for comparing with intervention outcomes.

3) Cost-effectiveness analysis of proposed intervention (PCT + NEWS2) in comparison with standard care.

i) Cost-effectiveness approach

Our CEA will be influenced by the assumption that the outcome on 28 day mortality of IA and SCA is non-inferior (no significant difference). It means that the CEA will in the first instance take the nature of a cost-consequence (minimization) analysis and only the costs of interventions (IA and SCA) need to be compared to find the cost-effective alternative [42, 44]. Here, sepsis care with lower costs (i.e. intervention costs), defined by cost per screened patient and cost per sepsis patient treated will be considered as the more cost-effective alternative.

ii) Cost-utility analysis

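### The first-step cost-minimisation rule ranks the arms on two measures with no precedence, and one of them divides by an undefined count fixed only after randomisation

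*Protocol*

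**What the plan says.** Section 18.2.1, point 3 i), starts from non-inferior 28-day mortality. On that footing, "the CEA will in the first instance take the nature of a cost-consequence (minimization) analysis", in which the arms are set against each other on intervention costs alone. The arm with lower costs, "defined by cost per screened patient and cost per sepsis patient treated will be considered as the more cost-effective alternative".

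The rule therefore joins two measures with *and*. The protocol does not define a sepsis patient treated and gives no order of precedence between the measures.

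Two other places bear on this:

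- Section 18.2 says of the economic analyses: "They will follow the intention-to-treat of the primary clinical effectiveness and safety analyses".
- Section 16.2 says "Currently around 90% of patients managed as suspected sepsis receive antibiotics" and, of the target, "A reduction by 10 percentage points to 80% would be considered a success". Lowering intravenous antibiotic initiation is the primary objective (5.1) and a co-primary outcome (5.3).

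**The concern.** An arm comparison on an intention-to-treat basis divides by the number randomised, which the intervention cannot change. A count of patients treated is fixed only after randomisation. If treated means started on antibiotics, the count is close to the co-primary outcome itself. An intervention that achieves its aim then has a smaller denominator, and its cost per treated patient rises even when it spends no more overall.

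The rule can then give two answers. PCT care can be cheaper per screened patient and dearer per treated patient on the same data, and the protocol does not say which result earns the label of more cost-effective. The denominator could be settled after the data are seen. Cost-effectiveness is a stated secondary objective (5.2), and this comparison is its planned first step if mortality proves non-inferior.

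**Working it through.** **Inputs.** Antibiotic initiation of 90% in control and 80% under PCT (section 16.2). The smallest effect detectable at 7002 patients is "a reduction from 90% to 87.6% prescriptions, with 90% power" (same section). Allocation is 1:1 (6.1). The protocol gives no cost figures, so the £1,000 and the 5% saving below are assumptions for illustration. I take *screened* to mean *randomised*, since patients belong to an arm only once randomised.

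**Check of the plan's own figure.** Section 16.2 says: "To detect such an effect with 90% power and two-sided 5% significance level the sample size required is 532". With pooled variance under the null, the number per arm is

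[1.960 × √(2 × 0.85 × 0.15) + 1.282 × √(0.90 × 0.10 + 0.80 × 0.20)]² / 0.10² = 265.9, rounded up to 266.

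Twice 266 is 532, an exact match, so the 90% and 80% are the rates the plan was sized on.

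**Formula.** If *treated* means started on antibiotics:

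cost per treated patient = cost per randomised patient / proportion treated.

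Let s be the proportional saving per randomised patient with PCT. Then

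ratio of cost per treated patient, PCT to control = (1 − s) × p(control) / p(PCT).

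The ratio equals 1 at s = 1 − p(PCT)/p(control). For s between 0 and that value, PCT is cheaper per screened patient and dearer per treated patient.

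| Initiation, control to PCT | Ratio at equal cost per randomised patient | Saving needed to tie per treated patient |
|---|---|---|
| 90% to 80% (target) | 0.90/0.80 = 1.125 | 1 − 0.80/0.90 = 11.1% |
| 90% to 85% (assumed) | 0.90/0.85 = 1.059 | 1 − 0.85/0.90 = 5.6% |
| 90% to 87.6% (smallest detectable) | 0.90/0.876 = 1.027 | 1 − 0.876/0.90 = 2.7% |
| No fall | 1.000 | 0% |

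**Illustration at 90% to 80%.** At an assumed £1,000 per randomised patient in both arms, cost per treated patient is 1,000/0.90 = £1,111 in control and 1,000/0.80 = £1,250 with PCT. If PCT saves an assumed 5% (£950), cost per treated patient is 950/0.80 = £1,187.50, a ratio of 0.95 × 1.125 = 1.069. PCT is 5% cheaper on one measure and 6.9% dearer on the other.

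The factor 1.125 needs no cost assumption and does not depend on which costs enter the numerator. If PCT costs more per screened patient, the two measures agree on the order and the denominator only widens the gap.

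**Other readings of the term.**

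- *Everyone managed as suspected sepsis.* This is in effect the randomised population. The ratio at equal spending is 1.000, and the measure largely repeats cost per screened patient.
- *Final diagnosis of sepsis.* Randomisation balances true sepsis in expectation, but the label is given after randomisation in an open-label trial where only the intervention arm has a PCT result (6.1, 10). Equal counts are not assured. Table 1 in section 11.1 lists no final sepsis diagnosis among the outcome data collected.

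**The case against.** The strongest reply is that the size of the effect depends on a reading the protocol does not state. The economic section elsewhere works with sepsis incidence and episodes of care, and with correct and false diagnoses, which fits a diagnostic meaning of the term at least as well. Section 4 says the aim is not to keep antibiotics from patients who require them. This stands: the 12.5% is conditional on treated meaning started on antibiotics.

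Even on that reading, 90% to 80% may overstate the shrinkage. The co-primary outcome is intravenous initiation at 3 hours, while later intravenous starts are a separate outcome (5.4) and oral antibiotics are also recorded (Table 1). Patients who start later are still treated. This also stands, and is why the range down to 2.7% belongs with the headline figure.

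A reader might infer that the economic evaluation as a whole is tilted against PCT. The documents do not support that. Cost per screened patient is named first in the same sentence and is undistorted if it means per randomised patient; at equal spending it gives a tie. Because the measures are joined by *and*, a conflict may yield no winner rather than a verdict against PCT. The rule applies only as a first step. The cost-utility analysis sets QALYs against incremental cost between arms, and the cost-benefit analysis counts avoided antibiotic use as a benefit. Neither divides by patients treated.

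It can also be said that definitions and precedence belong in an analysis plan. That would answer a complaint about missing detail. Here the protocol itself states a ranking rule, and the rule as written can contradict itself.

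**Conclusion.** The point holds for the first-step cost-minimisation rule. It uses two measures without precedence, and one rests on an undefined post-randomisation count that fits poorly with the intention-to-treat commitment in section 18.2.

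If *treated* means started on antibiotics, PCT looks 12.5% dearer per treated patient at equal spending under the planned 90% to 80%, and the measures disagree for any saving between 0 and 11.1%. At 87.6% the penalty is 2.7% and the range of disagreement is 0 to 2.7%. If it means everyone managed as suspected sepsis, there is no distortion. If it means a final diagnosis, the size cannot be derived from the documents, but the count is still assigned after randomisation. The departure from intention to treat is likewise conditional: it does not arise if the denominator is everyone managed as suspected sepsis.

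The clinical co-primary analyses are untouched. The change is worth making because a modest cost saving could otherwise be reported two ways from the same data.

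**What to change.** Amend the sentence in section 18.2.1, point 3 i):

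- Rank the arms on mean cost per randomised patient, by intention to treat, with a confidence interval for the difference between arms.
- Remove cost per sepsis patient treated from the decision rule. Define the term and report the figure by arm as a description only.

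The same wording should go into the economic analysis plan. The ranking measure needs no new data. The cost is one sentence in the protocol and a matching line in that plan.

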Cost-Utility Analysis (CUA) of non-inferiority trials has been conducted elsewhere [45]. For decision making from the analysis, cost-effectiveness planes prove to be a valuable tool in the interpretation of the results in an economic equivalence or non-inferiority trial [45]. We consequently will conduct a CUA due to the expected non-inferiorly health outcomes between IA and SCA. Health outcomes (QALYs) between IA and SCA will be compared with incremental costs of intervention between the arms. To assess QALYs gained in each patient group, the EQ-5D-5L instrument will be used on each patient (or representative if the patient is not in a condition of responding) under investigation of this study at screening, the 28th day, and 90th day after randomization. All primary and secondary empirical outcomes will be compared against existing literature and systematic reviews [27, 46, 47] and other trial-based studies. If possible, a meta-analysis will be carried out. The different in costs of interventions in IA and SCA and change in health outcomes (QALYs gained) will be plotted in cost-effectiveness plane for interpreting the results of this non-inferiority trial [45].

iii) Decision-tree analysis

Using data on health outcome (QALYs) and economic outcome (Cost of intervention) and probability of correct diagnosis (including false positives and false negatives) by both procedure arms (IA and SCA) will be used for conducting probabilistic analyses based on a decision-tree using TreeAge Pros (TreeAge Company, Inc) and STATA in a probabilistic CEA. Here, patients are randomly drawn from the IA and SCA treatment arm datasets in a MonteCarlo procedure, until convergence to stable estimates. The patients may face adverse effects of treatment with antibiotics in both arms and consequently worse health status. Patients correctly treated may face different outcomes in terms of cure and health status change and related resources. All resource use, including those of complications will be related to specific costs of NHS services. Following the TreeAge pathways using transition probability distributions between health states, based on the in-trial findings and literature, costs and health utility (health status) we shall be able to estimate expected societal and health care costs and expected utility of the patients (expressed in QALYs placed in IA and SCA).

4) Cost-benefit analysis

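### Section 18.2.1 uses one intervention cost for four economic analyses, and no single definition of it is right for all of them

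*Protocol*

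**What the plan says.** The protocol abbreviates the PCT arm as IA and the standard care arm as SCA.

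- **Point 2 (cost saved per pound invested)** measures the cost: "The costs of intervention will be captured by identifying and quantifying the inputs used for patients in IA and SCA". It then gives the cost its role: "Incremental costs between IA and SCA will constitute the investment on the proposed intervention for comparing with costs saved". Savings on antibiotics and admissions are the other side of that comparison. Point 2 also carries the cost forward: "this intervention cost will be used in the cost-effectiveness analysis (CEA", and names the cost-benefit analysis as a further use.
- **Point 3 i) (cost-minimisation)** assumes non-inferior mortality and picks the cheaper arm: "sepsis care with lower costs (i.e. intervention costs), defined by cost per screened patient and cost per sepsis patient treated".
- **Point 3 ii) (cost-utility)** uses the same term twice: "Health outcomes (QALYs) between IA and SCA will be compared with incremental costs of intervention between the arms", and "The different in costs of interventions in IA and SCA and change in health outcomes (QALYs gained) will be plotted in cost-effectiveness plane".
- **Point 3 iii) (decision tree)** names the cost of intervention as its economic outcome, but then attaches NHS costs to all resource use, complications included, and estimates expected societal and health care costs.
- **Point 4 (cost-benefit)** counts avoided antibiotics, bed days and productivity loss as benefits. It sets them against the incremental intervention cost of point 2 and calls the intervention useful if the benefits are larger.

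Section 18.2 commits the economic analyses to NHS and societal perspectives, with NHS and patient costs considered where applicable. Cost-effectiveness is a secondary objective (section 5.2).

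**The concern.** Points 2 and 4 compare an outlay with what it saves, so they need a cost that excludes the savings. A cost-minimisation rule and the cost axis of a cost-effectiveness plane need the opposite: the full difference in cost between the arms, savings and extra costs included. Section 18.2.1 says in terms that the first quantity is also used for the second purpose.

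The mechanism under test is avoided antibiotic treatment and what follows from it. A cost term that leaves this out cannot show whether the test pays for itself. A cost term that includes it makes the cost-benefit rule too lenient. Because the wording can be read both ways, the choice could be made after the data are seen.

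**Working it through.** The protocol states no price, cost difference or cost-effectiveness ratio, so there is no figure to reproduce. The check is algebraic, with assumed prices to show size.

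**Inputs**
- The intervention arm is standard management plus PCT-guided assessment (sections 9.4.2 and 16.1). Control patients have no PCT test (section 10).
- Antibiotic effect: 90% to 80%, the reduction that section 16.2 counts as a success, so 0.10 initiations avoided per patient.
- B = the other inputs per patient, c = PCT cost per patient, s = downstream saving per patient (negative if PCT care raises later use).
- Assumed, not from the protocol: c from £10 to £50, and a from £50 to £1,000 saved per avoided initiation, so s = 0.10 × a. Only savings linked to avoided initiations are counted here.

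**Reading 1: the investment, kept apart from savings (point 2)**

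With other delivery inputs equal, the difference is (B + c) - B = c. The term s does not appear. In 3 i) standard care is then the cheaper arm per screened patient, and in 3 ii) the cost axis shows +c, whatever happens to antibiotics, admissions or ICU days.

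**Reading 2: all inputs per arm**

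The difference is (B + c - s) - B = c - s, which can take either sign.

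Difference in £ per patient, PCT arm minus control:

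| c | Reading 1 | a = 50 (s = 5) | a = 200 (s = 20) | a = 500 (s = 50) | a = 1,000 (s = 100) |
|---|---|---|---|---|---|
| 10 | +10 | +5 | -10 | -40 | -90 |
| 20 | +20 | +15 | 0 | -30 | -80 |
| 30 | +30 | +25 | +10 | -20 | -70 |
| 50 | +50 | +45 | +30 | 0 | -50 |

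The four right-hand columns are Reading 2. Break-even is a = c / 0.10: £100 at c = £10 and £500 at c = £50. If s is negative the omission works the other way: with c = 20 and s = -10, Reading 1 gives +20 and Reading 2 gives 20 + 10 = +30.

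**What Reading 2 does to points 2 and 4**

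Take the benefits to be the same s.
- Correct cost-benefit rule: s > c.
- Rule with the cost already net of savings: s > c - s, that is 2s > c, or s > c/2.
- Example with c = 30 and s = 20. The correct rule asks whether 20 > 30, and fails; the PCT arm costs £10 more per patient. The double-counted rule asks whether 20 > 30 - 20 = 10, and passes.
- Point 2 on the same figures: saving per pound invested is 20/30 = 0.67 if counted once, and 20/10 = 2.00 if counted twice. At c = s = 20 the divisor is zero and the ratio is undefined.

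**Which parts each reading fits**

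| Part of section 18.2 | Reading 1 | Reading 2 |
|---|---|---|
| NHS and societal perspectives | conflicts | fits |
| Point 2 | fits | double counts |
| 3 i) and 3 ii) | downstream costs omitted | fits |
| 3 iii), all resource use costed | conflicts | fits |
| Point 4 | fits | double counts |

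**The case against.** The strongest reply is that the wording is loose and a full-cost reading is open. Point 2 captures inputs in both arms. Control patients have no PCT test, so the term cannot mean test cost alone. Point 2 also allows these costs to be taken from a UK study whose title refers to sepsis care. Point 3 i) speaks of sepsis care and of a cost per sepsis patient treated. Section 18.2 promises NHS and societal perspectives. All of this stands. It makes Reading 2 available, but that reading moves the fault to points 2 and 4.

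Second, even on Reading 1 the delivery inputs may differ between arms. Section 10 ties senior review, blood tests and fluids to risk category, which PCT helps to set. The cost per sepsis patient treated may also change with its denominator. This stands too: a difference of exactly c applies per patient with other inputs equal.

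Third, savings are not lost from the economic work as a whole. Points 2 and 4 report them and 3 iii) costs all resource use. That is correct, and it limits the consequence to 3 i) and 3 ii).

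Fourth, item lists are commonly left to a later analysis plan. That covers which items are costed. It does not cover the rule, fixed in the protocol, that the cost set against savings in point 2 is also the cost term of point 3.

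**Conclusion.** The point holds as an inconsistency in a stated rule: the intervention cost that section 18.2.1 shares between points 2, 3 i), 3 ii) and 4 cannot be correct for all four. On point 2's own definition, 3 i) and 3 ii) omit downstream savings or extra costs, and with other delivery inputs equal the per-patient difference is the PCT cost. On the full-input reading, 3 i) and 3 ii) are sound, but the cost-benefit threshold falls from c to c/2. Neither result needs a price. The pound figures rest on assumed prices and illustrate size only.

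A reader might infer that PCT care must come out dearer whatever the trial observes, that it has no chance of being the cheaper arm, or that every cost per QALY is overstated. The protocol does not support these. The first two need the narrow reading and equal delivery inputs, and the decision tree in 3 iii) does cost all resource use. The third presupposes net savings; if PCT care raised later use, leaving that use out would understate the cost.

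The issue affects a stated secondary objective and does not touch the co-primary analyses. It should be corrected before the economic analysis is run.

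**What to change.** - **Points 3 i) and 3 ii):** make the cost term the between-arm difference in total cost per randomised patient, for each stated perspective. Include the PCT test, antibiotics, hospital and ICU days, readmissions and other recorded resource use, plus patient costs for the societal view. Use this difference in the cost-minimisation comparison, on the cost-effectiveness plane and in the cost per QALY.
- **Points 2 and 4:** keep PCT delivery cost as a separately named term used only here, so that savings are counted once. List which items belong to delivery cost and which to savings.
- **Point 3 iii):** replace the cost of intervention label with the total cost that the decision tree goes on to use.

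This is a change of wording in section 18.2.1 and in any health economics analysis plan. The resource-use data are already to be collected (Table 1 and section 11.2). The downside is a wider interval on the cost difference, because total costs vary more between patients than test costs do.
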